#### **9.7.2.2. Prevalence of contra-indications and new restrictions**

We will assess the effectiveness of the RMM identified (started in May/2013 and finalized in March/2014) using interrupted time series analyses. In such methods, the coefficient and p-value for a change in secular trends of drug use (regarding both contraindications and restrictions/indications) after both time points/interventions is used to quantify the effectiveness of the proposed RMM. In these analyses, the *transitional* period going from start to finalization of the RMM (June/2013 to March/2014) will be used as a 'lag time' preceding the *assessment* period (April/2014 onwards).

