### 7.2. Regulatory action

In the frame of 13th PSUR assessment, data submitted raised concern regarding cardiovascular safety beyond the already recognized risk for venous thromboembolism. Analysis of pooled data from randomized studies in around 7,500 post-menopausal women with osteoporosis showed an increased risk of myocardial infarction with Protelos/Osseor as compared with placebo (1.7% versus 1.1 %), with a relative risk of 1.6 (95% CI, 1.07 to 2.38), and an increased risk of venous thrombotic and embolic events — 1.9% versus 1.3 % with a relative risk of 1.5 (95% CI, 1.04 to 2.19).

As a result of this assessment, an increased risk for serious cardiac disorders, including myocardial infarction has been identified and risk minimization measures specifically targeting this identified risk were recommended by the CHMP. These risk minimization measures included a restriction of the target population by excluding patients with established, current or past history of ischaemic heart disease, peripheral arterial disease and/or cerebrovascular disease and/or uncontrolled hypertension, and restricting the indication to severe osteoporosis in postmenopausal women at high risk for fracture to reduce the risk of vertebral and hip fractures and the treatment of severe osteoporosis in adult men at increased risk of fracture. Patients with significant risk factors for cardiovascular events (e.g. hypertension, hyperlipidaemia, diabetes mellitus and smoking) should only be treated with strontium ranelate after careful consideration. In addition, strontium ranelate therapy should only be initiated by a physician with experience in the treatment of osteoporosis. These changes were disseminated in the form of a DHPC in May 2013.

In view of this newly identified risk of serious cardiac disorders, an overall benefit/risk review under Article 20 of regulation (EC) No 726/2004 started in May 2013 and was finalized on 20 February 2014 ([EMA/112925/2014, 2014](#)). This led to a restriction of the indication to patients (postmenopausal women and men) with severe osteoporosis at high risk of fracture for whom treatment with other medicinal products approved for the treatment of osteoporosis is not possible due to, for example, contraindications or intolerance. As part of RMM, a new DHPC was disseminated in March 2014.

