### 9.3.2. Contra-indications and new indications

#### CONTRA-INDICATIONS

- History of Ischemic heart disease (IHD): myocardial infarction, angina pectoris, coronary artery bypass surgery (diagnoses or nitrate use) in year prior to SR therapy initiation.
- History of Peripheral arterial disease (PAD) in year prior to SR therapy initiation.
- History of transient ischemic attack (TIA) or stroke (ischemic or haemorrhagic) in year prior to SR therapy initiation.
- Uncontrolled hypertension, defined by MAH as the combination of the following: 1.previous diagnosis of hypertension coded in electronic medical records; 2.documented use of any anti-hypertensive therapy (either at that time or in the previous year before SR therapy initiation); and 3. at least two readings of Systolic Blood Pressure  $\geq 150$  or Diastolic Blood Pressure  $\geq 95$  mmHg recorded in the 3 months prior to SR therapy initiation.
- History of thromboembolic events (pulmonary embolism and deep venous thrombosis) in year prior to SR therapy initiation.

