### ***New restrictions***

Prevalence of each of the new restrictions for indication will be estimated on a patient level (new and prevalent users of SR) by age, sex, period and country. 95% Confidence Intervals will be estimated using a binomial distribution.

Interrupted time series analyses with segmented linear regression will be carried out to assess the impact of the RMM on these, as described above. Primary outcomes of interest will be proportion of SR users with: 1. A history of previous osteoporotic fracture/s or a “high estimated fracture risk” (as defined above); 2. Therapy initiation by a physician experienced in the treatment of osteoporosis (as defined above). 3. SR use not in first line (as defined above).

These analyses will be conducted separately for prevalent and incident SR users.

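### For second-line use, the June 2013 to March 2014 lag runs before the restriction was communicated, and the listed model terms do not isolate a change in April 2014

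*Protocol*

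**What the plan says.** Protocol section 7.2 dates two sets of measures. The first set restricted the target population by "excluding patients with established, current or past history of ischaemic heart disease, peripheral arterial disease and/or cerebrovascular disease and/or uncontrolled hypertension", limited the indication to severe osteoporosis and required an experienced prescriber. Of this set it says "These changes were disseminated in the form of a DHPC in May 2013". The second set came from the benefit/risk review finalized on 20 February 2014. It confined use to patients "for whom treatment with other medicinal products approved for the treatment of osteoporosis is not possible due to, for example, contraindications or intolerance", and section 7.2 adds: "As part of RMM, a new DHPC was disseminated in March 2014".

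Section 9.7.2.2 then gives one time structure to all interrupted time series: reference up to May 2013, transition from June 2013 to March 2014, assessment from April 2014. The transitional "period going from start to finalization of the RMM (June/2013 to March/2014) will be used as a 'lag time". The coefficient for a change in trend "after both time points/interventions is used to quantify the effectiveness of the proposed RMM". The model terms, listed under contra-indications, are a starting level, a prior trend, one level change located in the transitional months, and one trend change following the intervention. Under new restrictions the same method is applied to three primary outcomes, the third being "SR use not in first line (as defined above").

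**The concern.** A lag lets an intervention already announced take effect. For second-line use nothing of that kind had been announced in June 2013, so the ten transitional months are not a lag for this outcome. Its assessment period opens in the month after the March 2014 letter, with no time for uptake. The May 2013 measures, by contrast, get ten months.

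The model description adds a second difficulty. It speaks of two interventions but lists one level change and one trend change, so it does not say which term captures April 2014. The purpose of the study is to judge whether these measures worked. If the terms are not tied to the right date, a change in second-line use may be attributed to the wrong measure, or a real response to the 2014 restriction may be reported as a smaller one.

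**Working it through.** **The plan's own figures.** Section 9.5.1 gives 383 users for a prevalence of 53.1% with precision of 5 points: 1.96² × 0.531 × 0.469 / 0.05² = 382.7, so 383. The figure reproduces, but it concerns the precision of one prevalence, not a change over time. For the time series, section 9.5.1 relies on a rule of at least 10 points before and 10 after for 80% power. That power cannot be recomputed, because no effect size or variance is given.

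**Month counts.** Reference, January 2004 to May 2013: 9 × 12 + 5 = 113 (SIDIAP from January 2006: 89). Transition: 10. Assessment from April 2014: 9, 21 or 33 months with data to December 2014, 2015 or 2016. These end dates are assumed from the three extraction waves and the update table in section 6.

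**Models**, fitted by least squares to noise-free monthly percentages starting at 45%:

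- A, the listed terms read literally: intercept, trend, level change from June 2013, slope change from April 2014.
- B, transitional months left out: intercept, trend, level and slope change at April 2014.
- C, two breaks: level and slope change at June 2013 and again at April 2014, all months kept.
- D, own lag: reference to March 2014, April 2014 to January 2015 left out, level and slope change at February 2015.

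Effect sizes are assumptions. A constant background trend would not alter the results, since every model contains one. The range for A reflects whether April 2014 is coded as month 0 or month 1 of the slope term.

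Level change in points, then slope change in points per month:

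| Assumed truth | Model | 9 months | 21 months | 33 months |
|---|---|---|---|---|
| +15 step, April 2014 | A | 2.33–3.05; 1.99–2.09 | 4.81–5.25; 0.70 | 6.45–6.75; 0.37 |
| +15 step, April 2014 | B, and C at April 2014 | 15.0; 0 | 15.0; 0 | 15.0; 0 |
| Drift of 1 per month, June 2013 to March 2014, then flat | B | 10.0; 0 | 10.0; 0 | 10.0; 0 |
| +10 reached over 10 months from April 2014 | B, and C at April 2014 | 1.0; 1.00 | 3.6; 0.43 | 5.4; 0.20 |
| +10 reached over 10 months from April 2014 | D | not estimable | 10.0; 0 | 10.0; 0 |

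For the drift, C places level +1 and slope +1 at June 2013, and level −1 and slope −1 at April 2014. It locates the rise in the transitional segment and marks its end, where B shows only a 10-point level change for the assessment period.

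**Points left after an own lag.** With ten months from April 2014, assessment starts in February 2015. That leaves 0, 11 or 23 points to December 2014, 2015 or 2016. The last two meet the minimum of 10.

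**Precision cost of C.** Take the square roots of the diagonal of (X′X)⁻¹ with 33 later months, independent errors and unit residual standard deviation. The standard error of the April 2014 level term is 0.76 under C and 0.40 under B, a ratio of 1.9.

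**The case against.** The strongest reply is that section 9.7.2.2 treats the risk minimization measures as one package, begun in May 2013 and completed in March 2014. On that footing a rise during the transition is part of the package effect, and comparing reference with assessment is the right contrast. This stands for the package question. It does not tell the reader whether the 2014 restriction itself changed second-line use, and the reference to both interventions suggests that more than one is to be assessed.

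A reader might infer that the break for this outcome is simply misdated. The documents do not support that without a condition. Assessment begins in April 2014, the correct side of the March 2014 letter, and with the transitional months left out an immediate step is recovered in full. Misdating arises only if the listed terms are fitted as written. The final parametrization may be in the statistical analysis plan, which is not shown.

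It is also fair that the two distortions belong to different models and cannot both occur, that the effect sizes are assumed, that prevalence by month and by period would show a rise in the transition, and that gradual uptake would enter the slope term and not be lost.

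A second tempting inference concerns "History of thromboembolic events (pulmonary embolism and deep venous thrombosis) in year prior to SR therapy initiation", which section 9.3.2 lists as a contra-indication and which is therefore tested. Section 7.2 does not name it among the 2013 measures and calls the risk already recognized; section 9.2.5.3 keeps it apart from the newly defined contra-indications. But no section dates that contra-indication, and the objective covers contra-indications generally. This supports interpreting the series separately, not removing it.

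**Conclusion.** The point holds for one primary outcome. On the protocol's own dates, second-line use has 0 full months of lag after its restriction was communicated, and 10 months up to and including that communication are handled as transition. This part rests on no assumption.

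The consequence depends on how the model is fitted. With the listed terms taken literally, an assumed +15-point step in April 2014 is split into about +6.5 to +6.7 points dated June 2013 and 0.37 points per month (33 later months). With the transitional months left out, that step is recovered without bias, but earlier drift cannot be told apart from the 2014 restriction, and a +10-point change spread over ten months shows a level term of 1.0, 3.6 or 5.4 points with 9, 21 or 33 later months. These sizes are illustrations, since the protocol gives no effect or variance for the time series. Either way the April 2014 term needs to be stated before the data are analyzed.

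**What to change.** For second-line use only, specify a two-break segmented model with level and slope terms at both June 2013 and April 2014, keeping the transitional months as their own segment. Take the April 2014 terms as the effect of the 2014 restriction. Read them beside the transitional slope, because the April slope term is measured against a trend resting on ten months.

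The two-break model alone does not cure gradual uptake. Add a sensitivity analysis with a prespecified lag after March 2014, its length stated in advance; even ten months is workable from the second extraction wave.

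Keep the reference-versus-assessment contrast and label it as the effect of the whole package. Bring the sentence on two interventions and the list of model terms into agreement. The other outcomes need not be re-dated here; note that severe osteoporosis was restated in the 2014 measures, so it does not belong to 2013 alone. Note also that venous thromboembolism history is not among the measures dated to 2013, and interpret its series separately.

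The cost is wording, two more parameters than a single-break model with level and slope terms, and a less precise April 2014 estimate (about 1.9 times the standard error for the level term under the assumptions above). No new data are required.

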#### ***Contra-indications***

Prevalence of each of the contraindications will be estimated on a patient level (new and prevalent users of SR) by age, sex, period and country. 95% Confidence Intervals will be estimated using a binomial distribution.

Interrupted time series analyses will be carried out to assess the impact of the RMM on these. Each contributing data source will be analyzed using an interrupted times series design (Kastner, 2011), using repeated measures before (up until May 2013) and after intervention (from April 2014 onwards), using a *transitional* lag time period (from June 2013 to March 2014, both included) to control for secular trends. Using this design, each database acts as its own control.

Using the interrupted times series approach, we estimate the trend in the prevalence rates in monthly intervals during the study period in the three analysis periods, and test for changes pre- and post- intervention, using the *transitional* period as a pre-specified lag time for the intervention to take effect on a) the overall (absolute rate) of outcome, and b) the slope of the trend in rates of outcome.

Segmented linear regression models will be used to estimate the monthly proportions of outcomes. Controlling for baseline level and trend, the models estimate changes in levels and trends of rates after the pre-defined interventions. The regression model includes terms to estimate the pre-existing level for each rate in the first months of the observation period (intercept), trend in the rate before the interventions were introduced, change in level of the rate during the transitional/lag time period, and change in trend after the intervention (Serumaga, 2011).

These analyses will be conducted separately for prevalent and incident SR users.

### ***New restrictions***

Prevalence of each of the new restrictions for indication will be estimated on a patient level (new and prevalent users of SR) by age, sex, period and country. 95% Confidence Intervals will be estimated using a binomial distribution.

Interrupted time series analyses with segmented linear regression will be carried out to assess the impact of the RMM on these, as described above. Primary outcomes of interest will be proportion of SR users with: 1. A history of previous osteoporotic fracture/s or a “high estimated fracture risk” (as defined above); 2. Therapy initiation by a physician experienced in the treatment of osteoporosis (as defined above). 3. SR use not in first line (as defined above).

These analyses will be conducted separately for prevalent and incident SR users.

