### **New indications/prescribing conditions**

Experienced prescriber; treatment not in first line; severe osteoporosis

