### PRIMARY OBJECTIVES:

#### Effectiveness of risk minimization

1. To characterise utilization patterns of strontium ranelate in three periods: up to May 2013 (*reference period*), from June 2013 to March 2014 (*transitional period*), and from April 2014 onwards (*assessment period*).
2. To estimate the prevalence of contraindications in SR users during the same three periods: up to May 2013 (*reference period*), from June 2013 to March 2014 (*transitional period*), and from April 2014 onwards (*assessment period*).

3. To calculate the prevalence of SR users who fulfil the new indications (after imposition of new restrictions of use) for SR therapy in these three periods: up to May 2013 (*reference* period), from June 2013 to March 2014 (*transitional* period), and from April 2014 onwards (*assessment* period).

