### 9.5.1. RMM effectiveness study

[figure not shown]
Based on published studies, the combined prevalence of MI, CVD and PAD before the DHPC published in May 2013 is assumed to be of 19.2% in female and 29.5% in male new users of SR (Abrahamsen, 2014).

A total of **320** male users of SR will suffice to estimate with a 95% confidence and an absolute precision of  $\pm 0.05$ , an unchanged prevalence of MI/CVD/PAD of 29.5%. Similarly, **239** female SR users would suffice to estimate with a 95% confidence and an absolute precision of  $\pm 0.05$ , an unchanged prevalence of MI/CVD/PAD of 19.2%.

Regarding the prevalence of new indication/restrictions of use (severe osteoporosis, and second line therapy), recent data suggest that the prevalence of these would range from 13.0% (Svanstrom, 2014) to 53.1% (Abrahamsen, 2014) for previous fragility fracture (severe osteoporosis), and from 40.4% (Svanstrom, 2014) to 47.9% (Abrahamsen, 2014) for the use of SR as a second line anti-osteoporosis treatment. Given this, 383 users of SR would suffice to estimate (with 95% confidence and 5% precision) an unchanged prevalence of 53.1% (most conservative scenario) for both indications. Lower numbers would be needed if this prevalence either increases or decreases (See Figure (9.5.1) 1).

A number of scenarios with different possible prevalence rates of MI/CVD/PAD, previous osteoporotic fracture, and use as a second line anti-osteoporosis therapy amongst SR users in subsequent years in the period before the publication of the DHPC in May 2013 (*reference*) and after the publication of the second DHPC from April 2014 onwards (*assessment* period) are presented in Figure (9.5.1) 1.

**Figure (9.5.1) 1 - Number of SR users required to estimate the prevalence of contraindications or new indication/restrictions with a 5% absolute precision**

[figure not shown]
For the interrupted time series analyses (see details below), sample size calculations are related to the estimation of the number of observations or time points at which data will be collected. According to the quality criteria of Ramsey et al, at least 10 pre- and 10 post-intervention data points would be needed to reach at least 80% power to detect a change (if the autocorrelation is  $>0.4$ ) (Ramsay, 2003). Our outcomes will be estimated at monthly intervals to ensure that  $>10$  data points are available for both the pre-defined *reference* and *assessment* analysis periods.

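### Objective 3 is answered restriction by restriction; the share of strontium ranelate users who meet the 2014 indication as a whole is not estimated

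*Protocol*

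**What the plan says.** Section 8 of the Protocol (and the Abstract) lists this as the third primary objective on risk minimization: "To calculate the prevalence of SR users who fulfil the new indications (after imposition of new restrictions of use) for SR therapy", in the reference, transitional and assessment periods.

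Section 7.2 gives the outcome of the 2014 review as a restriction to patients "with severe osteoporosis at high risk of fracture for whom treatment with other medicinal products approved for the treatment of osteoporosis is not possible". The rule that an experienced physician starts therapy is introduced in the same section as a further measure, dating from May 2013.

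The Abstract lists the new indications and prescribing conditions as three items: "Experienced prescriber; treatment not in first line; severe osteoporosis". Section 9.3.2 gives each item its own operational definition and no rule for combining them.

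Section 9.7.2.2, under New restrictions, then states: "Prevalence of each of the new restrictions for indication will be estimated on a patient level". For the interrupted time series it continues: "Primary outcomes of interest will be proportion of SR users with", followed by the three criteria as separate outcomes, analysed separately for incident and prevalent users. No section plans the proportion of users who meet the criteria together. The strata by number of contra-indications in the Abstract and section 9.7.3.2 belong to the safety incidence rates.

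**The concern.** The objective counts users who fulfil the indications, and the 2014 indication is a conjunction. A first-line user with a fracture is outside it, and so is a second-line user without severe osteoporosis. Yet each counts as a success in one of the planned series. Objective 2 is worded differently: it asks for the prevalence of contraindications among users, and one proportion per contraindication answers that. Section 9.7.2.2 applies the same one-proportion-per-item template to objective 3, where it does not give the share of use that conforms to the restricted indication.

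At stake is what the final report can say. It could describe how each restriction moved, but could not state what fraction of SR use falls within the 2014 indication.

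**Working it through.** **Inputs, all from section 9.5.1.** Previous fragility fracture: 13.0% to 53.1%. Second-line use: 40.4% to 47.9%. The lower two figures come from one cited Danish study and the upper two from another, so each pair belongs together. Precision target: 5 points either side at 95% confidence.

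**The plan's own sizes.** With n = z² p(1 − p) / d², z² = 3.8415 and d = 0.05:
- p = 0.531: 3.8415 × 0.2490 / 0.0025 = 382.67, so 383 (stated: 383)
- p = 0.295: 319.57, so 320 (stated: 320)
- p = 0.192: 238.38, so 239 (stated: 239)

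All three reproduce. Each concerns a single proportion. The statement "383 users of SR would suffice to estimate (with 95% confidence and 5% precision) an unchanged prevalence of 53.1"% is applied to severe osteoporosis and second-line use in turn, not to their combination.

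**What two separate proportions say about the joint one.** The share meeting both lies between max(0, p1 + p2 − 1) and min(p1, p2). If the criteria were independent it would be p1 × p2.
- Upper pair: 0.531 + 0.479 − 1 = 0.010, and the minimum is 0.479. Range 1.0% to 47.9%; 25.4% if independent.
- Lower pair: 0.130 + 0.404 − 1 is negative, so the lower limit is 0; the minimum is 0.130. Range 0% to 13.0%; 5.3% if independent.

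The ends of the upper-pair range in cells per 100 users:
- Low end: 1.0 meet both, 52.1 are severe and first line, 46.9 are second line and not severe, none meet neither.
- High end: 47.9 meet both, 5.2 are severe only, 46.9 meet neither.

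Both patterns give exactly the same two series.

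**Dependence on the inputs.** These figures are not the planned outcomes. Section 9.3.2 also counts a Garvan 5-year risk of at least 10% as severe osteoporosis, and a contra-indication or precaution for oral bisphosphonates as not first line. The planned proportions may therefore be higher. Higher values narrow the range but do not close it: at 80% on both criteria, 0.80 + 0.80 − 1 gives 60% to 80%; at 90% on both, 80% to 90%. With three criteria at 80% each, the share meeting all of them is 40% to 80%.

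**Users needed for a joint proportion.** The largest requirement at 5-point precision is at p = 0.5: 3.8415 × 0.25 / 0.0025 = 384.15, so 385, against the 383 already planned for.

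**The case against.** The best reply is that the Protocol uses the plural for a list. The Abstract lists three items, section 9.3.2 defines each alone, section 9.5.1 sizes severe osteoporosis and second-line use separately, and the title table states the aim as the prevalence of contraindications and restrictions. On that usage section 9.7.2.2 does deliver objective 3, criterion by criterion. This stands, and it rules out saying that the objective goes unanswered. The separate series also have value of their own: the restrictions came in steps in 2013 and 2014, and only component series show which one changed practice. The smallest of them also caps full conformity.

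Three stronger readings are tempting, and the documents do not support them.

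- A reader might infer that the indication also includes the experienced prescriber and the absence of contraindications. Section 7.2 joins only severe osteoporosis and other treatment not being possible. The prescriber rule is a prescribing condition, and contraindications have their own objective and time series.
- A reader might infer that conformity could fall while every series improves. If both upper figures rose by 10 points, to 63.1% and 57.9%, the joint share could be 21.0% to 57.9%, and 21.0% is below 25.4%. But that needs a move from independence to the strongest possible negative association. Nothing in the documents suggests such a move, and the fall would be 4.4 points, inside the 5-point precision.
- A reader might infer that all components are cleanly held for each patient. Section 9.3.2 says that some criteria rest on proxies open to misclassification. The primary-care prescriber item is a caseload measure of the GP, and Garvan risk is available only where age and either bone density or weight are recorded.

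**Conclusion.** The point holds in a limited form. Objective 3 is answered for each restriction and not for the 2014 indication as a whole, because no joint proportion is planned and the separate ones do not determine it. On the Protocol's illustrative figures the undetermined range is 46.9 points wide (1.0% to 47.9%) for the upper pair and 13.0 points (0% to 13.0%) for the lower pair. The widths rest on fracture-only and second-line-only figures and will differ under the full definitions. The non-identification does not depend on those values, although it shrinks if the component proportions approach 100%.

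This is not a detail left for the statistical analysis plan: the Protocol itself fixes the separate proportions as the primary outcomes. It is worth correcting, but it does not invalidate the component analyses.

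**What to change.** In section 9.7.2.2, under New restrictions, add a patient-level outcome: severe osteoporosis AND not first line, each as defined in section 9.3.2. Estimate it by period and country, separately for incident and prevalent users, with the same interrupted time series. Report it alongside the three component series, which stay as primary outcomes.

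Versions that also require an experienced prescriber, or no contraindication, can be secondary and limited to databases where those items are measurable. Uncontrolled hypertension, for example, needs two blood pressure readings within 3 months, and the Aarhus description in section 9.4.4 mentions no blood pressure data.

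The cost is one derived variable and one more series per database, with essentially no more users needed. The real drawback is that a composite of proxies compounds misclassification, so its level may differ between databases for data reasons. The report should say so.

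If the joint outcome is not added, reword objective 3 in section 8 and the Abstract to refer to each of the new indications or restrictions, and state that full conformity with the indication is not estimated.
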